1. REPORTING & ANALYSIS PLAN SYNOPSIS

Overview	Key Elements of the RAP
Purpose	
 This RAP describes the planned analyses and output to be included in the Clinical Study Report for Protocol 201492.
Protocol	
 This RAP is based on the protocol amendment 2 [(Dated: 15/Jan/2016) of study 201492 (GSK Document No.: 2014N205225_02] and eCRF Version 1.0.
Primary Objective	
 Establish the efficacy of FFNS 55 µg and 110 µg QD versus vehicle placebo nasal spray in paediatric subjects (ages 2 to 12 years old) with AR.
Primary Endpoint	
 Mean change from baseline over the first 2 weeks treatment period in daily, reflective total nasal symptom scores (rTNSS) in subjects ages 2 to 12 years old.
Study Design	
 This study will be a randomized, double-blind, placebo-controlled, multicentre parallel study. The study will be comprised of screen, run-in period (4 to 14 days), treatment period (28 days) and follow up period (3 to 7 days). During the study period, all investigators, subjects and GlaxoSmithKline (GSK) personnel remain blinded. Subjects will be assigned to randomized treatments in a 1:1:1 ratio, in accordance with a computer generated randomization schedule provided by GSK. The randomization will be centralized and stratified by age (≥ 2 to ≤ 6 years old and >6 to ≤ 12 years old) and by classification of AR (intermittent vs. persistent) to ensure treatment balance in age groups and AR classification groups for both safety and efficacy assessments.
Planned Analyses	
 All decisions regarding final analysis, as defined in this RAP document, will be made prior to Database Freeze (unblinding) of the study data.
Analysis Populations	
 The All Subjects Enrolled Population comprise of all subjects, for whom a record exists on the study database, including screen/run-in failures and any subject who was not screened but experienced an SAE between the date of informed consent and the planned date of the Screening Visit. This population will be used for reporting subject disposition, reasons for screen/run-in failures, and inclusion, exclusion and randomization criteria deviations and SAEs for non-randomized subjects. The intent-to-treat (ITT) population is defined as all randomized subjects who received at least one dose of study drug. This population will be the primary analysis population for safety and efficacy analysis. Subjects will be assessed according to the treatment they are randomized to. The Subset ITT population (2 to 6 years old) is defined as a subset of ITT population comprising subjects aged ≥ 2 to ≤ 6 years old. The per-protocol (PP) population is defined as all randomized subjects in ITT population who do not have any full protocol deviations. This population will be

Overview	Key Elements of the RAP
	
used for supportive analysis of the primary efficacy endpoint only. The PP population will not be analysed if this population comprises more than 95% or less than 50% of the ITT population.
 
 • All the summary and analysis will be performed for both ITT population and Subset ITT population (2 to 6 years old). The ITT, Subset ITT and PP populations will be determined prior to unblinding of the study (except for the PD of incorrect treatment container ID, which can be determined only after unblinding).
Hypothesis	
 • No formal hypothesis test will be done in this study. All the results from analysis modelling are for descriptive purpose.
Primary Analyses	
 • The mean change from baseline over the first 2 weeks treatment period in daily rTNSS (rhinorrhea, nasal congestion, nasal itching, and sneezing) will be analyzed using the method of pairwise comparison of treatment groups (active vs. placebo) with analysis of covariance (ANCOVA) adjusting for baseline daily rTNSS, classification of AR (IAR or PER), age (as continuous variable), gender, and treatment.
Secondary Analyses	
 • Regarding the secondary analyses for diary card endpoints (rTOSS over 2 weeks, rTOSS and rTNSS over 4 weeks), the analysis method will be the same as the primary efficacy analysis. • Overall evaluation of response to therapy for subjects will be summarized, and analysed using logistic regression adjusting for age (as continuous variable), gender, classification of AR (IAR or PER), and treatment. • ANCOVA model adjusting for baseline nasal finding score by anterior rhinoscopy, classification of AR (IAR or PER), age (as continuous variable), gender, and treatment will be used to analyse nasal finding score by anterior rhinoscopy. • ANCOVA model adjusting for classification of AR (IAR or PER), age (as continuous variable), gender, and treatment will be used to analyse the mean rescue-free days over the first 2 weeks and over the 4 weeks treatment.

2. SUMMARY OF KEY PROTOCOL INFORMATION

2.1. Changes to the Protocol Defined Statistical Analysis Plan

There were no changes or deviations to the originally planned statistical analysis specified in the protocol (Dated: 15-JAN-2016).

2.2. Study Objective(s) and Endpoint(s)

Objectives	Endpoints
Primary Objectives	Primary Endpoints

 To establish the efficacy of FFNS 55 µg and 110 µg QD versus vehicle placebo nasal spray in paediatric subjects (ages 2 to 12 years old) with AR 	
 Mean change from baseline over the first 2 weeks treatment period in daily, reflective total nasal symptom scores (rTNSS) in subjects ages 2 to 12 years old
	Secondary Endpoints
	
 Overall evaluation of response to therapy (evaluated on a 7-point categorical scale) after the first 2 weeks treatment (day15)
	
 Mean change from baseline of intranasal finding score by anterior rhinoscopy at the first 2 weeks (day 15)
	
 Mean change from baseline over the first 2 weeks treatment period in the daily, reflective total ocular symptoms score (rTOSS)
	
 Rescue loratadine use (mean rescue-free days) over the first 2 weeks treatment period
	
 Mean change from baseline over the 4 weeks treatment period in daily rTNSS
	
 Overall evaluation of response to therapy after 4 weeks treatment period (day 29)
	
 The mean change from baseline of intranasal finding score by anterior rhinoscopy at the end of treatment (day 29)
	
 Mean change from baseline over the 4 weeks treatment period in the daily rTOSS

 Rescue loratadine use (mean rescue-free days) over the entire 4 weeks treatment period 	
Secondary Objectives	Safety Endpoints

 To investigate the safety of FFNS 55 µg and 110 µg QD versus vehicle placebo nasal spray in paediatric subjects (ages 2 to 12 years old) with AR 	
 Frequency and type of clinical adverse events
	
 Results of clinical laboratory tests (haematology, chemistry and urinalysis)
	
 Results of physical and nasal examination
	
 Vital signs (systolic and diastolic blood pressures, pulse rate and respiratory rate)

2.3. Study Design

Overview of Study Design and Key Features	

The diagram illustrates the study design timeline. It begins with a Run-in phase from Day -14 to -4. At Day 1 (Visit 2), randomization occurs. The study is divided into three treatment arms: 55µg Fluticasone Furoate Nasal Spray (OD), 110µg Fluticasone Furoate Nasal Spray (OD), and Placebo Nasal Spray (OD). The treatment period lasts from Day 1 to Day 29 (Visits 3, 4, and 5). After Day 29, there is a Follow-up phase with No Treatment until Day 36 (Phone contact). A legend indicates that a circle with 'R' represents Randomization.
	
Design Features	
 Randomized, Double-Blind, Placebo-Controlled, Multicentre parallel Study to Evaluate the Efficacy and Safety of Once-Daily, Intranasal Administration of Fluticasone Furoate Nasal Spray 55 µg and 110 µg for 4 Weeks in Chinese Paediatric Subjects Ages 2 to 12 Years old with Allergic Rhinitis
Dosing	
 Subjects will be randomized on Day 1 to receive 55 µg FF from device A + 55 µg placebo from device B, or 55 µg FF from device A + 55 µg FF from device B, or 55 µg placebo from device A + 55 µg placebo from device B Inhale one spray in each nostril from each nasal spray device in the morning
Treatment Assignment	
 Approximately 360 subjects will be randomized 1:1:1 to receive FFNS 110 µg, FFNS 55 µg, or placebo The randomization will be centralized and stratified by age (2 to ≤6 years old and 6 to ≤12 years old) and by classification of AR (IAR vs. PER) to ensure treatment balance in age groups and AR classification groups
Interim Analysis	
 No interim analysis is planned.

2.4. Statistical Hypotheses

The study is designed to provide an estimated mean treatment difference between active drug groups and placebo group in primary efficacy endpoint, change from baseline of daily rTNSS over the first 2 weeks treatment period. No formal hypothesis test will be done. All the results from analysis modeling are for descriptive purpose.

The primary comparisons of interest between treatment groups are:

FFNS 55 µg vs Placebo

FFNS 110 µg vs Placebo

As a supportive comparison, the pooled active drug groups (low and high-dose) will be compared with placebo.

3. PLANNED ANALYSES

3.1. Interim Analyses

No interim analysis is planned.

3.2. Final Analyses

The final planned primary analyses will be performed after the completion of the following sequential steps:

1. All subjects have completed the study as defined in the protocol.
2. All required database cleaning activities have been completed and final database release and database freeze has been declared by Data Management.
3. All criteria for unblinding the randomisation codes have been met.
4. Randomisation codes have been distributed according to RandAll NG procedures.

4. ANALYSIS POPULATIONS

Population	Definition / Criteria	Analyses Evaluated
All Subjects Enrolled	
 • Comprise of all subjects, for whom a record exists on the study database, including screen/run-in failures and any subject who was not screened but experienced an SAE between the date of informed consent and the planned date of the Screening Visit. 	
 • Reporting subject disposition, reasons for screen/run-in failures, and inclusion, exclusion and randomization criteria deviations and SAEs for non-randomized subjects
Intent-To-Treat	
 • Comprise of all randomized subjects who received at least one dose of study treatment. • Subjects will be analyzed according to the treatment they were randomly assigned to. • Any subject who receives a treatment randomization number will be considered to have been randomized. • The decision to exclude a subject from the ITT Population will be made prior to breaking the blind. 	
 • The primary analysis population for efficacy analysis • Safety analysis • Summary of demographic and baseline
Subset Intent-To-Treat (2 to 6 years old)	
 • Comprise of all subjects in the ITT Population aged ≥ 2 to ≤ 6 years old 	
 • The analysis population for efficacy and safety on subjects aged ≥ 2 to ≤ 6 years

Population	Definition / Criteria	Analyses Evaluated
		old 
 Summary of demographic and baseline on subjects aged ≥ 2 to ≤ 6 years old
Per-Protocol	
 Comprise of all randomized subjects in ITT population who do not have any full protocol deviations. Subjects identified as partial protocol violators will be included in the PP Population but will have their data excluded from PP analyses from the time of violation onwards. The definition of full and partial violations will be included in Section 4.1 (Protocol Deviations) and Appendix 1 (Protocol Deviation Management and Definition for Per-Protocol Population). The decision to exclude a subject from the PP Population or a subject's data from PP analyses will be made prior to breaking the blind (except the PD of incorrect treatment container ID, which only can be defined after unblinding). 	
 The supportive analysis population for primary efficacy endpoint only. The PP population will not be analyzed if this population comprises more than 95% or less than 50% of the ITT population.

4.1. Protocol Deviations

- Important protocol deviations (including deviations related to study inclusion/exclusion criteria, conduct of the trial, patient management or patient assessment) will be summarised and listed.
- Important deviations which result in exclusion from the analysis population will also be summarised and listed. (Please refer to Appendix 1: Protocol Deviation Management and Definitions for Per Protocol Population).
- Protocol deviations will be tracked by the study team throughout the conduct of the study in accordance with the Protocol Deviation Management Plan.
- Data will be reviewed prior to unblinding and freezing the database to ensure all important deviations and deviations which may lead to exclusion from the analysis are captured and categorised on the protocol deviations dataset.
- This dataset will be the basis for the summaries and listings of protocol deviations.

- A separate summary and listing of all inclusion/exclusion/randomisation criteria deviations will also be provided. This summary will be based on data as recorded on the inclusion/exclusion/randomisation page of the eCRF.

5. CONSIDERATIONS FOR DATA ANALYSES AND DATA HANDLING CONVENTIONS

Table 1 provides an overview of appendices within the RAP for outlining general considerations for data analyses and data handling conventions.

Table 1 Overview of Appendices

Section	Component
11.1	Appendix 1: Protocol Deviation Management and Definitions for Per Protocol Population
11.2	Appendix 2: Time & Events
11.3	Appendix 3: Assessment Windows
11.4	Appendix 4: Treatment States and Phases
11.5	Appendix 5: Data Display Standards & Handling Conventions
11.6	Appendix 6: Derived and Transformed Data
11.7	Appendix 7: Premature Withdrawals & Handling of Missing Data
11.8	Appendix 8: Values of Potential Clinical Importance
11.9	Appendix 9: Multicentre Studies
11.10	Appendix 10: Examination of Covariates, Subgroups & Other Strata
11.11	Appendix 11: Multiple Comparisons & Multiplicity
11.12	Appendix 12: Model Checking and Diagnostics for Statistical Analyses
11.13	Appendix 13: Abbreviations & Trade Marks
11.14	Appendix 14: List of Data Displays
11.15	Appendix 15: Example Mock Shells for Data Displays

6. STUDY POPULATION ANALYSES

6.1. Overview of Planned Analyses

The study population analyses will be based on the Intent-To-Treat population and subset Intent-To-Treat population, unless otherwise specified.

Table 2 provides an overview of the planned study population analyses, with full details of data displays being presented in Appendix 14 List of Data Displays.

Table 2 Overview of Planned Study Population Analyses

Display Type	Data Displays Generated		
	Table	Figure	Listing
Subject Disposition			
Summary of Screening Subject Disposition	Y		
Reasons for Exclusion from the Per Protocol Population	Y		Y
Number of Subjects by Centre	Y		
Subject Accountability: End of Study Record	Y		
Subject Withdrawals: End of Study Record			Y
Number of Subjects at Each Visit	Y		
Protocol Deviations			
Inclusion/ Exclusion/Randomisation Criteria Deviations	Y		Y
Important Protocol Deviations	Y		Y
Date of and Reason for Breaking Treatment Blind During the Study			Y
Demography			
Demographics Characteristics	Y		Y
Medical Condition			
Summary of Allergy History	Y		Y
Summary of Baseline Nasal Symptom Scores	Y		
Summary of Medical Conditions	Y		Y
Concomitant Medication			
Relationship between ATC Level 1, Ingredient and Verbatim Text	Y		
Summary of Concomitant Medications	Y		Y
Treatment Compliance			
Treatment compliance	Y		

NOTES :

- Y = Yes display generated.
- All summaries tables will be presented by treatment group.

7. PRIMARY STATISTICAL ANALYSES

7.1. Efficacy Analyses

7.1.1. Overview of Planned Efficacy Analyses

The primary efficacy analyses will be based on the Intent-To-Treat population (of primary interest), PP population (supportive if appropriate) and the subset ITT-2 to 6 years old population (supportive), unless otherwise specified.

Table 3 provides an overview of the planned efficacy analyses, with full details of data displays being presented in Appendix 14: List of Data Displays.

Table 3 Overview of Planned Efficacy Analyses

Endpoints	Absolute								Change from Baseline							
	Stats Analysis			Summary		Individual			Stats Analysis			Summary		Individual		
	T	F	L	T	F	F	L	T	F	L	T	F	F	L		
Primary Efficacy Analyses																
Baseline Daily Reflective Total Nasal Symptom Scores				Y			Y									
Daily Reflective Total Nasal Symptom Scores				Y			Y				Y	Y		Y		
Mean Daily Reflective Total Nasal Symptom Scores over Each Week				Y			Y	Y			Y	Y		Y		
Mean Daily rTNSS over the First 2 Weeks				Y			Y	Y			Y			Y		
Mean Daily rTNSS over the 4 Weeks Treatment				Y			Y	Y			Y			Y		

NOTES :

- T = Table, F = Figure, L = Listing, Y = Yes display generated.
- Stats Analysis = Represents TFL related to any formal statistical analyses (i.e. modelling) conducted.
- Summary = Represents TFL related to any summaries (i.e. descriptive statistics) of the observed raw data.
- Individual = Represents FL related to any displays of individual subject observed raw data.
- All the tables will be presented by treatment group.

7.1.2. Planned Efficacy Statistical Analyses

Primary Statistical Analyses
Endpoint(s)

 • Mean change from baseline of Daily rTNSS over Each Week • Mean change from baseline of Daily rTNSS over the First 2 Weeks • Mean change from baseline of Daily rTNSS over the 4 Weeks
Model Specification

 • Endpoints will be statistically analyzed using analysis of covariance (ANCOVA) model adjusting for baseline daily rTNSS, classification of AR (IAR or PER), age (as continuous variable), gender and treatment. • No imputations will be performed on missing daily diary data.
Model Checking & Diagnostics

 • Refer to Appendix 12: Model Checking and Diagnostics for Statistical Analyses.
Model Results Presentation

 • LS mean change from baseline values for each treatment group will be presented with their associated standard errors. • Estimated treatment differences along with corresponding 95 % confidence intervals (CIs) and p-values will be presented for the treatment comparisons.
Sensitivity and Supportive Statistical Analyses

 • The summaries, figures and analysis detailed in Section 7.1.1 (Overview of Planned Efficacy Analyses) and above primary statistical analyses, will be repeated for the PP population and subset ITT (2 to 6 years old) population.

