4. STUDY DESIGN

4.1. Overall Design

Protocol waivers or exemptions are not allowed with the exception of immediate safety concerns. Therefore, adherence to the study design requirements, including those specified in the Time and Events Table (Table 2), Section 7.1, are essential and required for study conduct.

- This phase IV study will be a randomized, double-blind, placebo-controlled, multicenter parallel study.
- Eligible subjects will participate in the study which begins with a 4 to 14-day run-in period with no treatment (Visit 1).
- After a minimum 4-day run-in period, subjects meeting the randomisation criteria will be randomised in a 1:1:1 ratio to the following three treatment arms (Visit 2);, in accordance with a computer generated randomization schedule provided by GlaxoSmithKline (GSK), via an Interactive Voice Response System (IVRS) called Registration and Medication Ordering System (RAMOS).
 - FFNS 110 µg once daily
 - FFNS 55 µg once daily
 - Vehicle placebo aqueous nasal spray
- The randomization will be centralized and stratified by age (≥ 2 to ≤ 6 years and > 6 to ≤ 12 years) and by classification of AR (intermittent vs. persistent) to ensure treatment balance in age groups and AR classification groups for both safety and efficacy assessments. Subjects with 6 years old and less than 7 years old will be treated as 6 years of age; these subjects will be analysis in group of 2 to 6 years. Subjects with 12 years old and less than 13 years old will be treated as 12 years of age and will be analysis in group of 6 to 12 years.
- Following the 28-day treatment period, subjects will be followed up by telephone contact within 5 ± 2 days after the last dose. The following procedures will be performed: Adverse Event (AE)/ Serious Adverse Event (SAE) assessment. Subjects will be discharged from the study upon completion of the follow-up phone call.

In summary, this study is comprised of screen, run-in period (4 to 14 days), double-blind treatment period (28 days) and follows up period (3 to 7 days). Subjects entering the study will participate for maximum of 50 days, including five clinical visits and a follow-up telephone contact.

Figure 1 Study Design

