5.1. Inclusion Criteria

A subject will be eligible for inclusion in this study only if all of the following criteria apply:

[1] Informed Consent
1. Subject's parent/guardian has provided with an appropriately signed and dated informed consent.
[2] Outpatient
2. Chinese subject is treatable on an outpatient basis
[3] Gender
3. Both Male and Female

[4] Age

4. Subjects must be ≥ 2 to ≤ 12 years of age at Visit 2.

Only premenarchal female subjects (of non-child bearing potential) are eligible to participate in this study.

[5] Diagnosis of AR

5. Subjects were diagnosed as IAR or PER according to the criteria for the diagnosis and classification of [[Chinese Guideline for Diagnosis and Treatment of AR in Pediatrics, 2011](#)].

Criteria for the diagnosis of AR:

1. **Symptoms:** subjects must have 2 or more symptoms of AR (watery rhinorrhea, nasal obstruction, nasal itching and sneezing), which are also present consecutively or accumulatively more than 1 hour on each day prior to Visit 1, or/and concomitant ocular symptoms: ocular itching, red eyes, watery eyes etc. .
2. **Physical signs:** nasal mucosa pale, oedema, nasal secretion. Allergic shiner and allergic crease in severity pediatric
3. **Laboratory test:**
 - I. **Skin Prick Test (SPT)*:** must represent a positive response using standardized allergen extract.
 - II. **Serum-specific IgE test*:** represent a positive response using standardized allergen extract.

(*allergen must be aeroallergen)

Diagnosis: subjects have nasal symptoms described above or/and associated with ocular symptoms, as well as the nasal signs and one of laboratory test positive or documents.

Documents: that demonstrate SPT represented a positive response OR serum-specific IgE testing represented a positive response within 12 months prior to Visit 1.

Criteria for classification of AR:

- Intermittent AR, IAR: the symptoms are present < 4 days a week, OR for < 4 weeks.
- Persistent AR, PER: the symptoms are present ≥ 4 days a week, OR for ≥ 4 weeks.

[6] Exposure

6. Subject must be willing to maintain the same environment throughout the study

[7] Ability to Comply with Procedures

7. Subject and/or subject's parent/guardian understands and is willing, able and likely to

comply with study procedures and restrictions as well as manage study drug administration

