6.2.2. Assignment of Randomisation/Treatment Pack Numbers

At Visit 2, subjects meeting the randomisation eligibility criteria will be assigned to study treatment via a telephone call to the RAMOS. During the call, the site will confirm the subject's **Subject Number** and the RAMOS will then assign two additional numbers:

1. **Treatment Kit Numbers** that identifies the double-blind medication to be dispensed to the subject from the investigators inventory; and
2. A **Randomisation Number** from the study randomisation schedule created by GSK. Once assigned, this number must not be reassigned.

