11.6.2. Study Population

Demographics

Age

- GSK standard IDSL algorithms will be used for calculating age where birth date will be imputed as follows:
 - Any subject with a missing day will have this imputed as day '15'.
 - Any subject with a missing date and month will have this imputed as '30th June'.
 - Age will be calculated based on the screening date.
- Birth date will be presented in listings as 'DDMMMYYYY'.

Body Mass Index (BMI)

- Calculated as $\text{Weight (kg)} / [\text{Height (m)}^2]$

Treatment Compliance Based on Subject Diary Card

The number of doses of study drug taken during the double-blind treatment period will be estimated based on information recorded by the subject on the diary card. Subjects will document their study

Treatment Compliance Based on Subject Diary Card

medication administration/compliance on the diary card by answering the question “Did you spray 2 sprays of your medication in each nostril?” Each occurrence of “yes” in response to this question will count as one dose of study medication. Percent treatment compliance will be calculated for each subject as follows:

$$\% \text{ Treatment Compliance} = \frac{\text{\# of doses used}}{\text{expected \# of doses used}} \times 100\%, \text{ where}$$

- # of doses used = sum of the “yes” responses to the question “Did you spray 2 sprays of your medication in each nostril?” for all days on treatment
- expected # of doses used = # of days on treatment.

Overall compliance will be categorised as follows:

- < 80%
- ≥ 80% to ≤120%
- >120%.

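### The randomised age stratum is not a term in the ITT ANCOVAs, and Subset ITT has no stated age source or date

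*SAP*

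**What the plan says.** **Strata.** Protocol 4.1 has randomisation "stratified by age (≥ 2 to ≤ 6 years and > 6 to ≤ 12 years) and by classification of AR". The same bullet counts a child aged 6 but not yet 7 as 6 and places that child in the younger group, so the working boundary is the seventh birthday. The SAP synopsis gives the same strata. SAP 2.3 restates them as "stratified by age (2 to ≤6 years old and 6 to ≤12 years old", and those two groups overlap at age 6.

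**Models.** SAP 7.1.2 adjusts for baseline, AR classification, "age (as continuous variable), gender and treatment". In the code in SAP 11.12.1, age is not in the CLASS statement and there is no age-group term. The ANCOVAs for rTOSS, rhinoscopy score and rescue-free days in SAP 8.1.2 treat age the same way. Protocol 9.4.1 lists age without saying whether it is continuous or grouped.

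**Dates.** Protocol 5.1 sets eligibility by "years of age at Visit 2". Protocol 6.2.2 places treatment assignment at the same visit: "At Visit 2, subjects meeting the randomisation eligibility criteria will be assigned to study treatment via a telephone call to the RAMOS". SAP 11.6.2 says: "Age will be calculated based on the screening date". Under Protocol 4.1 the two visits are 4 to 14 days apart.

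**Subset.** SAP 4 defines Subset ITT as the ITT children aged 2 to 6. It names neither the recorded stratum nor the derived age as the source.

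**The concern.** There are two separate gaps.

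First, a factor used to restrict the randomisation is normally carried into the analysis. Here one of the two stratification factors (AR class) is, and the other appears only through a straight line in age. A linear term cannot represent a step in symptom change at the stratum boundary. If such a step exists, the part the line misses stays in the residual variance and the intervals in the linear models are slightly wider than they need to be.

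Second, a child whose seventh birthday falls in the run-in is 6 at screening and 7 at Visit 2. If the stratum uses age at Visit 2 and the subset uses the SAP-derived age, that child is randomised in the older stratum and counted in the younger subset. Similarly, a child who turns 2 in the run-in is eligible at Visit 2 but under 2 by the SAP derivation. The 2-to-6 group is the protocol's named subgroup of interest, and the summaries and analyses are to be repeated in it, so its membership rule feeds many tables.

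**Working it through.** **1. The plan's own precision figure.** Protocol 9.2.1 gives SD 2.6, with 100 evaluable children per arm overall and 50 per arm in the subset. Half-width = t(0.975, 2n−2) × SD × √(2/n).

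- n = 100: 1.9720 × 2.6 × √0.02 = 0.7251 (stated 0.725).
- n = 50: 1.9845 × 2.6 × √0.04 = 1.0319 (stated 1.032).

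Both reproduce.

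**2. How much of the stratum linear age already carries.** Assume half the children are spread uniformly over ages 2 to under 7 and half over 7 to under 13.

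- Group means are 4.5 and 10, so the between-group variance is (5.5/2)² = 7.5625.
- The average within-group variance is (25/12 + 36/12)/2 = 2.5417.
- R² = 7.5625/(7.5625 + 2.5417) = 0.748.

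Linear age therefore carries about 75% of the stratum indicator.

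**3. Variance left over if there is a step.** Extra residual variance as a share of SD² = step² × 0.25 × (1 − 0.748)/2.6².

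- 1-point step: 0.063/6.76 = 0.9%.
- 2-point step: 0.252/6.76 = 3.7%.

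The corresponding half-width multipliers are √1.0093 = 1.0047 and √1.0373 = 1.0185. Applied to 0.723, they give about 0.726 and 0.736.

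**4. Simulation check.** 3,000 stratified trials were simulated per scenario, with 100 per arm (50 per arm in each age stratum), SD 2.6, and true effects of −0.5 (110 µg) and −0.3 (55 µg). Age was modelled in completed years. Baseline, gender and AR class were left out. The age effects are assumptions, because the documents give none. Estimate and coverage are for 110 µg versus placebo.

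| Age effect assumed | Half-width, linear age only (as in SAP) | Half-width, linear age plus stratum | Estimate, as in SAP | Coverage, as in SAP |
|---|---|---|---|---|
| None | 0.7232 | 0.7242 | −0.4998 | 95.9% |
| Linear, 0.2 points/year | 0.7233 | 0.7243 | −0.4996 | 95.9% |
| 0.5-point step | 0.7240 | 0.7242 | −0.4995 | 95.9% |
| 1-point step | 0.7265 | 0.7242 | −0.4991 | 95.8% |
| 2-point step | 0.7362 | 0.7242 | −0.4984 | 95.9% |

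The no-effect value is just below the protocol's 0.725 because the residual variance is pooled over three arms (quantile 1.968 instead of 1.972). The largest loss is 0.7362 − 0.7242 = 0.012. With no step, the extra term costs 0.001.

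**5. Children who could change group.** Expected number = children per year of age × run-in days/365.25. The density near age 7 is not given, so three assumptions were used:

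- 360/11 = 32.7 per year (even spread over ages 2 to 12).
- 180/5 = 36 per year (the protocol minimum of 60 per arm in the younger group).
- 216/5 = 43.2 per year (60% of all children in the younger group).

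The lowest figure is 32.7 × 4/365.25 = 0.4 and the highest is 43.2 × 14/365.25 = 1.7. At 36 per year and a 9-day run-in it is 0.9.

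**The case against.** The case for leaving the plan alone is fair, and much of it stands. Age is in every model. The protocol prespecifies age as a covariate, and the SAP fixes its form before unblinding. A continuous term also uses age differences within strata, which a two-level factor discards. The gain from adding the stratum depends on a step for which the documents give no evidence. The 1- and 2-point steps are two and four times the 0.5-point effect assumed for 110 µg. Any loss is in the conservative direction. The study is descriptive, so no test decision depends on it. Within the 2-to-6 subset the stratum is constant and its omission changes nothing.

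Three stronger readings are tempting but unsupported.

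- **That the analysis departs from the randomised groups.** SAP 4 analyses ITT children by assigned treatment. SAP 11.5.3 makes actual treatment the reporting default only where nothing else is stated, and the ITT definition states otherwise.
- **That the standard-error argument extends to the logistic model.** It does not. Adding a prognostic covariate to a logistic regression generally raises the standard error of the log odds ratio and changes the conditional quantity being estimated.
- **That the documents send a child to one stratum and the other subset.** No section states the date of the age used for stratification. Visit 2 is inferred from Protocol 5.1 and 6.2.2. SAP 11.6.2 gives its age rule under demographics and does not say that it decides Subset ITT.

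These limits reduce the point to a minor one. They do not remove the missing term, the two different age dates, or the unnamed source for the subset.

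**Conclusion.** The point holds as a minor, low-cost improvement. The ITT ANCOVAs omit the age stratum as a factor, and the plan leaves the age source and date for Subset ITT open. The treatment comparison is not biased by this: estimates stay within 0.002 of the true −0.50, and coverage is 95.8% to 95.9% in every scenario examined. The precision at stake is nil without a step at the boundary and at most 0.012 on a half-width of about 0.724 for a 2-point step. Those figures assume SD 2.6, 100 evaluable children per arm, an even age split, and age effects chosen for illustration. Misplacement in the subset is expected for about one child, and only if the stratum uses age at Visit 2 while the subset uses the screening-based age.

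**What to change.** - In SAP 7.1.2, 8.1.2 and the ANCOVA code in 11.12.1, add the age stratum recorded at randomisation as a class variable in the ITT ANCOVAs, keeping continuous age. Omit it in the Subset ITT models, where it is constant.
- In SAP 4, define Subset ITT by that recorded stratum.
- In SAP 11.6.2, compute age at the Visit 2 date.
- Reconcile the overlapping strata in SAP 2.3 with Protocol 4.1, including the protocol's rule that children under 7 count as 6.

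The cost is SAP wording and 1 df. With 300 evaluable children the SAP model has seven parameters (intercept, two for treatment, and one each for baseline, AR class, gender and age), so residual df fall from 293 to 292. No new data are needed. The logistic model needs no change on this ground.
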